Participants in MG0007 will remain on their gMG background medications. With the exception of steroids and acetylcholinesterase (AChE) inhibitors, all gMG medication doses should be maintained during each respective 6-week treatment cycle and efforts should be made to maintain a stable dose during the first 8 weeks of the Observation Period.

Study participants who receive rescue therapy (intravenous immunoglobulin [IVIg], plasma exchange [PEX], subcutaneous immunoglobulin [SCIg], or iv corticosteroid) during the Treatment Period are not eligible to receive any further treatment with rozanolixizumab. Study participants must complete the first 8 weeks of the Observation Period after the last dose of rozanolixizumab prior to completing the EOS visit assessments, and subsequently will be withdrawn from the study (Section 4.4).

Those patients who received rescue therapy (IVIg, PEX, SCIg, or iv corticosteroid) during the observation or no treatment with rozanolixizumab periods may continue in the study at the Investigator's discretion and after discussion with Medical Monitor and/or UCB Study

Physician. The following cycle of rozanolixizumab should in general not start earlier than 4 weeks following the last dose of IVIg, SC Ig, or iv corticosteroids or the last PEX session, unless there is a medical reason, and an earlier treatment initiation is being considered █ for the study participant as agreed upon with the Medical Monitor and/or UCB Study physician.

Study participants (not withdrawn from the study) will continue in MG0007 until product approval or until transition to a managed access program (MAP), if available, as indicated per the Sponsor, and according to local guidance. For country-specific requirements, see Appendix 8, Section 10.8.

Number of Participants

No formal sample size calculation can be performed. All eligible study participants from MG0003 and MG0004 will be invited to participate in MG0007. It will be assumed that approximately 200 study participants will be enrolled into MG0007.

Treatment Groups and Duration

Fixed unit doses across body weight tiers and study arms will be employed in MG0007. This OLE study will continue treatment with rozanolixizumab sc fixed doses equivalent to approximately 7mg/kg and 10mg/kg administered QW for 6-week treatment cycles.

Table 1-1: MG0007 dose levels and weight tiers

[figure not shown]
Bodyweight	Rozanolixizumab dose eqv	
	7mg/kg Dose 1	10mg/kg Dose 2
≥35 to <50kg	280mg	420mg

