The dose may be adjusted to 7mg/kg or 10mg/kg at the beginning of each treatment cycle based on the Investigator's discretion. Rules for dose modification and temporary treatment hold are described in Section [6.6](#) and Section [6.7](#). The minimal time to start the next treatment cycle is 4 weeks following the last dose of the treatment period of the previous cycle. If a study participant requires treatment earlier than 4 weeks, IgG levels from the previous cycle should be considered and discussed with the Medical Monitor. A new treatment cycle **should not** be initiated until total IgG level is ≥ 2 g/L.

Participants in MG0007 will remain on their gMG background medications ([Table 6-3](#)). With the exception of corticosteroids and AChE inhibitors, all gMG medication doses should be maintained during each respective 6-week treatment cycle and efforts should be made to maintain a stable dose during the first 8 weeks of the Observation Period.

Study participants who receive rescue therapy (IVIg, PEX, SC Ig, or iv corticosteroid) during the Treatment Period are not eligible to receive any further treatment with rozanolixizumab, must complete an additional 8 weeks of follow up after the last dose of rozanolixizumab. Study participants must complete the first 8 weeks of the Observation Period after the last dose of rozanolixizumab prior to completing the EOS visit assessments, and subsequently will be withdrawn from the study (Section [4.4](#)).

Those patients who received rescue therapy (IVIg, PEX, SC Ig, or iv corticosteroid) during the observation or no treatment with rozanolixizumab periods may continue in the study at the Investigator's discretion and after discussion with Medical Monitor and/or UCB Study Physician. The following cycle of rozanolixizumab should in general not start earlier than 4 weeks following the last dose of IVIg, SC Ig, or iv corticosteroids or the last PEX session, unless there is a medical reason, and an earlier treatment initiation is being considered [REDACTED] for the study participant as agreed upon with the Medical Monitor and/or UCB Study physician.

Study participants (not withdrawn from the study; criteria outlined in Section [7.2](#)) will continue in the study and until product approval or until transition to a managed access program (MAP), if

available, as indicated per the Sponsor, and according to local guidance. For country-specific requirements, see Appendix 8 (Section 10.8).

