6.5.3 Treatments specific to NMJ interference

Treatments could interfere with the function of the NMJ (and which therefore could impair study participants with MG), such as, but not limited to, include the following medications:

- botulinum toxin
- aminoglycoside antibiotics
- tetracycline antibiotics
- penicillamine
- magnesium

For a more detailed list please refer to the Myasthenia Gravis Foundation of America (MGFA) medication list (<https://myasthenia.org/What-is-MG/MG-Management/Cautionary-Drugs>). The benefit-risk of starting these medications should be carefully considered by the Investigator, and where possible, the Investigator will discuss with the Medical Monitor and/or sponsor's Study Physician prior to initiating therapy that can affect the NMJ.

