6.5.4 Rescue medication

The study site will supply rescue therapy that will be obtained locally. Rescue therapy will be given as per standard of care and at the discretion of the Investigator. Study participants who continue to experience moderate to severe symptoms despite treatment with rozanolixizumab may be treated with the following as rescue therapy:

- IVIg
- SC Ig
- PEX, or plasmapheresis
- iv corticosteroids at a higher dose than previous oral dose

Participants who are treated with rescue therapy during the Treatment Period are not eligible to receive any further treatment with rozanolixizumab. Study participants must complete the first 8 weeks of the Observation Period after the last dose of rozanolixizumab prior to completing the EOS visit assessments, and subsequently will be withdrawn from the study (Section 4.4).

Those patients who received rescue therapy during the observation or no treatment with rozanolixizumab periods may continue in the study at the Investigator's discretion and after discussion with Medical Monitor and/or UCB Study Physician. The following cycle of rozanolixizumab should in general not start earlier than 4 weeks following the last dose of IVIg, SC Ig, or iv corticosteroids or the last PEX session, unless there is a medical reason, and an earlier treatment initiation is being considered █ for the study participant as agreed upon with the Medical Monitor and/or UCB Study physician.

The date and time of rescue medication administration as well as the name and dosage regimen of the rescue medication must be recorded.

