9. Study participant is treated with rescue therapy (IVIg, SCIG, PEX, or iv corticosteroids; see Section 6.5.4) during the Treatment Period. Those patients who received rescue therapy during the observation or no treatment with rozanolixizumab periods may continue in the study at the investigator's discretion and after discussion with Medical Monitor and/or UCB Study Physician. The following cycle of rozanolixizumab should in general not start earlier than 4 weeks following the last dose of IVIg, SCIG, or iv corticosteroids or the last PEX

session, unless there is a medical reason, and an earlier treatment initiation is being considered █ for the study participant as agreed upon with the Medical Monitor and/or UCB Study physician.

10. Study participant has a recurrence of aseptic meningitis (see also Appendix 14 [Section 10.14]).

Study participants **may** permanently discontinue rozanolixizumab **and** move into the Observation Period at the discretion of the Investigator, Medical Monitor, and Study Physician if any of the following events occur:

1. Study participant is noncompliant with the study procedures or medications in the opinion of the Investigator.
2. Study participant takes prohibited concomitant medications as defined in this protocol.

Investigators should contact the Medical Monitor, whenever possible, to discuss the withdrawal of a participant in advance. Investigators should attempt to obtain information on study participants in the event of withdrawal (eg, reason for withdrawal, any safety information).

In the event of study participant early withdrawal, the scenarios as described in Section 4.4 need to be considered.

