6.5.3 Treatments specific to NMJ interference	
A new section on treatments that may interfere with the function of the NMJ has been added.
	Updated to correct an inadvertent omission from the original protocol.
7.1.1 Liver chemistry stopping criteria	
New text specific to continued treatment with increased monitoring has been added.
	Updated to provide further clarity.
7.3 Lost to follow up	
The following text has been removed:
 
Investigators should contact the Medical Monitor, whenever possible, to discuss the withdrawal of a study participant in advance. Study participants who are withdrawn will not be replaced.
	Updated to remove duplication in previous section.
8.2.2 Vital signs	
Wording on blood pressure and pulse measurements has been removed.
	Updated to remove repetitive wording.

Section # and Name	Description of Change	Brief Rationale
8.2.5 Suicidal risk monitoring	Wording on the use of C-SSRS at specific timepoints has been removed.	Updated to be consistent with the study design and schedule of activities.
8.2.6 Assessment and management of TB and TB risk factors	
TB assessment by IGRA; the following updates have been made:
 
 - Baseline has been replaced with Screening. - Visit numbers in reference to MG0004 have been updated. - Added a cross reference to the schedule of activities. 
Wording on indeterminate IGRA tests result has been updated.
 
Test conversion: the following has been deleted, "The IGRA result must be negative for study participants to enroll in this study"
	Updated to be consistent with the study designs for MG0004, and MG0003 for the IGRA TB test to be performed at the Screening Visit, not the Baseline Visit.
8.3.3 Follow-up of AEs and SAEs	AESM and the associated cross reference have been added.	Updated to be consistent with remainder of protocol.
8.9 Biomarkers	This section has been updated to remove "2 hours" in reference to collection of additional samples and to update the severity of AESMs, as well as new examples of GI disorders.	Updated to be consistent with remainder of protocol.
8.9.1 Immunological assessments	New text has been added in specific to blood sampling for the measurement of COVID-19 antibodies.	COVID-19 antibodies will be collected in this study for all participants who have received a COVID-19 vaccine.

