10.13.2 Management of infusion reactions or hypersensitivity reactions

Study participants must be closely monitored for reactions during and after the study treatment administration period. Standard precautions must be taken for the study participants with regard to sc infusion complications. Suggested management guidelines for infusion-related reactions and anaphylaxis at the study site are provided in **Table 10-3**. Definitions of mild, moderate, and severe events will be consistent with CTCAE version 5.0 (Section 10.3).

Nurses administering the IMP at home should follow their own management guidelines, which should be reviewed and endorsed by the Investigator prior to first home administration.

Table 10-3: Suggested management guidelines for infusion reactions or anaphylaxis

Type of reaction	Suggested action
Acute – Mild Grade 1	Monitor vital signs every 10 min. If the reaction worsens to Grade 2, follow the instruction below.
Acute – Moderate Grade 2	Interrupt/hold infusion temporarily to further assess and initiate treatment if necessary. Consider the use of iv fluid and antihistamine iv/im. Consider administering paracetamol or NSAIDs. Monitor vital signs initially every 5 min. If the reaction improves and upon further assessment it is clear that the event is not an anaphylaxis, restart the infusion cautiously. Continue monitor vital signs every 5 minutes. If reaction recurs or worsens to Grade 3, discontinue infusion.
Acute – Severe Grade 3 or anaphylaxis	Discontinue IMP infusion permanently. Emergency care services. Maintain airway; ensure oxygen is available. Administer: 
– Antihistamine iv/im, corticosteroids iv, epinephrine im, and iv fluids as appropriate.– Monitor vital signs every 2 min.– Hospitalize, if condition not improving or worsens– Monitor patient until symptoms resolve.

CTCAE=Common Terminology Criteria for Adverse Events; im=intramuscular; IMP=investigational medicinal product; iv=intravenous(ly); NSAID=nonsteroidal anti-inflammatory drug

Note: Management criteria were adapted from the CTCAE v5.0 (National Cancer Institute, 2017).

Conditions in which anaphylaxis is likely should be diagnosed using Sampson's Criteria (Sampson et al, 2006. The infusion must be discontinued immediately, and emergency resuscitation measures implemented.

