6.4 Prior and concomitant medications

The number and percentage of participants taking Prior or Concomitant medications will be summarized using the SS by Anatomical Therapeutic Chemical (ATC) class, presenting as Anatomical Main Group (ATC Level 1), Pharmacological Subgroup (ATC level 3), Preferred Term (PT), actual treatment group, and RLZ total for entire study.

Additionally, rescue medications are those that are mentioned in Protocol section 6.5.3 and identified:

- if Rescue Medication is ticked as yes on CRF Concomitant Medication page
- Or PEX as procedure entered on CRF Concomitant Medical Procedure page

The start date of rescue medication should be on or after Baseline. All rescue medications will be summarized using the SS.

Medications classified as Prior or Concomitant will be listed using the FAS. A by-participant listing of concomitant procedures will also be listed using the FAS. Originally reported dates will be used for listings.

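### SAP 6.4 takes its rescue medications from the wrong protocol section, and the dose condition on iv corticosteroid rescue stands in only one of the places that define rescue

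*SAP*

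**What the plan says.** SAP 6.4 states that "rescue medications are those that are mentioned in Protocol section 6.5.3 and identified" in one of two ways: the rescue box ticked on the concomitant medication page, or PEX entered on the concomitant procedure page. The medications so defined are summarised on the Safety Set. SAP 11.2 defines use of rescue therapy by the same two CRF sources and cites no protocol section.

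The protocol section to which SAP 6.4 refers is "6.5.3 Treatments specific to NMJ interference". It names botulinum toxin, aminoglycosides, tetracyclines, penicillamine and magnesium as examples, and points to a longer outside list. Rescue medication is the next section, 6.5.4. That section lists IVIg, SCIg, PEX or plasmapheresis, and "iv corticosteroids at a higher dose than previous oral dose", for participants whose moderate to severe symptoms persist on rozanolixizumab.

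Elsewhere the iv corticosteroid item has no dose condition. The synopsis has "Study participants who receive rescue therapy (intravenous immunoglobulin [IVIg], plasma exchange [PEX], subcutaneous immunoglobulin [SCIg], or iv corticosteroid) during the Treatment Period", and SAP 2.3.1 gives the same list. Protocol 4.1 has "Study participants who receive rescue therapy (IVIg, PEX, SC Ig, or iv corticosteroid) during the Treatment Period are not eligible" for further rozanolixizumab. The mandatory stop, criterion 9 of protocol 7.1.4, reads "Study participant is treated with rescue therapy (IVIg, SCIG, PEX, or iv corticosteroids; see Section 6.5.4) during the Treatment Period": no condition in the words, but a pointer to the section that has one.

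**The concern.** There are two separate defects.

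The first is in the SAP. The 6.4 sentence joins the section list and the CRF identification with an and. A programmer who follows it literally needs a drug that is both in protocol 6.5.3 and ticked as rescue. The resulting table would disagree with the 11.2 table in the same report. SAP 11.6 repeats both tables for Japan.

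The second is in the protocol and carries into the SAP. Oral corticosteroids are permitted background treatment with no dose limit (Table 6-3) and are exempt from the stable-dose rule (4.1 and 6.5.1). An iv corticosteroid at or below the previous oral dose is therefore a conceivable event. The documents do not settle whether it is rescue.

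The rescue flag has several uses. Use of rescue and time to rescue are named endpoints. Rescue also censors time to MG-ADL response (SAP 9.6) and removes IgG values from the summaries for 8 weeks (10.2.1). In the Treatment Period, rescue ends rozanolixizumab permanently.

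**Working it through.** No arithmetic applies; the check is a comparison of the places that define or use rescue.

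| Place | Source of the rescue list | Dose condition on iv corticosteroid |
|---|---|---|
| Protocol 1.1, 4.1; SAP 2.3.1 | Own list: IVIg, PEX, SCIg, iv corticosteroid | None |
| Protocol 6.5.4 | Own list, with plasmapheresis added | Above the previous oral dose |
| Protocol 7.1.4, criterion 9 | Own list, plus a pointer to 6.5.4 | None in the words; present through the pointer |
| SAP 6.4 | Protocol 6.5.3, plus CRF tick or PEX procedure | Not addressed |
| SAP 11.2 | CRF tick or plasma exchange procedure | Not addressed |
| SAP 9.6, 10.2.1, 11.3 | No list or source of their own | Not addressed |

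**Step 1: the cross-reference.** None of the drugs or classes named in protocol 6.5.3 is a rescue therapy in any other row. Applied as written, SAP 6.4 admits no IVIg, SCIg or iv corticosteroid by name. It also conflicts with itself, because it identifies PEX, which 6.5.3 does not name.

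**Step 2: how the number may have arisen.** The amendment history under Protocol Amendment 1 (03 Mar 2021) records for 6.5.3 that "A new section on treatments that may interfere with the function of the NMJ has been added". That insertion would explain a number one too low. However, SAP Amendment 1 (24 Jun 2022) records adding the rescue definition to 6.4, which is after the protocol change, and SAP Amendment 2 (22 Feb 2024) left the number in place. Two SAP revisions have passed without correcting it.

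**Step 3: the same event under each protocol wording.** Take an iv corticosteroid given for MG symptoms in the Treatment Period at a dose not above the previous oral dose.
- Synopsis and 4.1, on their words alone: rescue, with no further rozanolixizumab.
- 6.5.4: not on the rescue list.
- 7.1.4 criterion 9: rescue on its words, not rescue if the pointer governs.

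Nothing in either document says which of these governs the CRF tick. The tick and the decision to stop are both made at the site, and different sections support different answers.

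**Step 4: where the flag goes.** SAP 6.4 and 11.2 share the tick-or-PEX rule. SAP 9.6, 10.2.1 and 11.3 name no other source, so on the text they use the same flag. An ambiguity in the tick then passes to all four analysis sections together.

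**Step 5: a smaller mismatch.** Protocol 6.5.4 lists plasmapheresis beside PEX. SAP 6.4 names only PEX and SAP 11.2 only plasma exchange, so a procedure recorded as plasmapheresis is not expressly covered.

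**The case against.** The case for leaving this alone has real force. SAP 6.4 gives a workable rule straight after the wrong section number, SAP 2.3.1 lists the right therapies, and no sensible programmer would tabulate magnesium as rescue. That makes the error easy to recognise, but 6.4 still needs correcting because it is the SAP's stated definition.

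It can also be said that the parentheses in the synopsis and 4.1 merely list forms of rescue, that 6.5.4 is the dedicated section, and that criterion 9 cites it. This is a fair reading and may be the intended one. However, the synopsis, 4.1 and SAP 2.3.1 give no pointer to 6.5.4 for the list, so a site using them does not meet the dose condition. CRF Completion Guidelines (protocol 10.1.6.1) may settle the tick; they are not among the documents. SAP 11.2 already lists the data of rescue users, which allows ticked entries to be reviewed but does not find unticked ones.

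Two stronger readings are tempting and should not be adopted. A reader might infer that the endpoints, the censoring and the IgG exclusion rest on different events. The text does not support that: one CRF rule stands in 6.4 and 11.2, and no other section departs from it. A reader might also infer that iv steroids for an infusion reaction lead to differing withdrawals, since Table 10-3 includes "Antihistamine iv/im, corticosteroids iv, epinephrine im, and iv fluids as appropriate". That row applies to Grade 3 reactions or anaphylaxis and already directs a permanent stop. Criterion 8 of 7.1.4 separately requires one for a severe or serious reaction needing corticosteroid. The rescue wording does not decide the stop there.

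**Conclusion.** Both defects stand. The SAP 6.4 reference is wrong and, taken literally, makes the 6.4 rescue summary contradict 11.2. The iv corticosteroid wording is inconsistent across the protocol, so the tick and the Treatment Period stop can be applied differently to the same event. The four analysis sections inherit that ambiguity through what appears to be a single flag; this rests on SAP 9.6, 10.2.1 and 11.3 using the 11.2 rule, which they do not state.

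The size of the effect cannot be given. Neither document reports how often rescue or iv corticosteroid is used, or at what dose relative to prior oral treatment, so any percentage range would have no anchor in the text. SAP 4.6 makes all analyses descriptive, so neither power nor type I error is involved. Rescue use and time to rescue are listed under the other endpoints, not the primary or secondary ones. This is a definitional correction to make before database lock, not a threat to the primary safety analysis.

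**What to change.** - In SAP 6.4, change the reference from protocol 6.5.3 to 6.5.4.
- State one rescue definition there, with plasmapheresis as in 6.5.4, and have SAP 9.6, 10.2.1, 11.2 and 11.3 cite it.
- Before lock, list for review the ticked entries that do not meet the definition and the unticked IVIg, SCIg and iv corticosteroid entries.
- Reconcile the iv corticosteroid wording in the synopsis, protocol 4.1, 6.5.4 and 7.1.4, and SAP 2.3.1. Which clinical wording applies is for the sponsor to decide.

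The cost is one section number, a short definition with four cross-references, one review listing, and harmonised protocol wording. A listing is proposed instead of an automatic derivation because the data for the latter are not shown to exist. Protocol 6.5.4 requires the name, dosage regimen, date and time of rescue, but does not mention route or indication. SAP 11.1 computes average daily dose by preferred term and gives no conversion between different steroids, so comparing an iv dose with a previous oral dose may need case-by-case judgement.

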6.4.1 Categories of prior and concomitant medications

Medications will be classified as follow based on imputed start and stop dates & times as outlined in [Section 4.2.2](#).

- **Prior** medications will include any medications that started before the first administration of MG0007 IMP.
- **Concomitant** medications will include any medications that have been taken at least once after the first administration of MG0007 IMP during the Treatment and/or Observation Period.

Medication Started	Medication finished	Classification
Before 1st Dose IMP	Any time	Prior
Any time	After 1st Dose IMP	Concomitant

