6.5 Concomitant medication(s)/treatment(s)

6.5.1 Permitted concomitant treatments (medications and therapies)

Concomitant medications listed in [Table 6-3](#) are permitted during the study for the treatment of gMG, and dose adjustments are allowed between treatment cycles. With the exception of corticosteroids and AChE inhibitors, the dose of permitted concomitant medications should be maintained during each 6-week treatment cycle and every effort should be made to maintain a stable dose during the first 8 weeks of each Observation Period. Any violation of the permitted treatment criteria would lead to prohibited treatment and should be discussed with the Investigator, Sponsor, and Medical Monitor.

If a study participant receives a COVID-19 vaccine, the product name and date of administration(s) should be captured in the eCRF as a concomitant medication.

Table 6-3: Permitted concomitant treatments

Permitted Medications	Dose
Oral corticosteroids (eg, prednisolone)	No specific requirements
Methotrexate	≤30mg/week
Mycophenolate mofetil	≤3g/day
Cyclosporine ^a	≤5mg/kg/day for unmodified ≤4mg/kg/day for modified (microemulsion)
Azathioprine	≤3mg/kg/day
Cholinesterase inhibitors	≤600mg pyridostigmine/day
Tacrolimus ^b	≤5mg/day

^a Doses higher than listed are permissible if trough level is ≤300ng/mL.

^b If the total daily weight-based dose is >5mg, then a plasma trough level should be checked to ensure study participant is not above the recommended therapeutic range.

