2.1.3 Other objectives

- To assess the pharmacokinetics (PK) of rozanolixizumab
- To evaluate the incidence and emergence of antidrug antibody (ADA) of rozanolixizumab
- To assess the pharmacodynamics (PD) of rozanolixizumab
- To assess the effects of rozanolixizumab on the concentration of [REDACTED]
[REDACTED]
- To assess the need for gMG medications including changes in type and doses
- To assess the effect of rozanolixizumab on [REDACTED]
[REDACTED]

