3.2.2 Study periods

The study cycle consists of the following:

- Treatment Period: 6 weeks
- Observation Period: 16 weeks
- Non-treatment period

The following definitions for starting and entering the study periods for each cycle will be applied:

- **Treatment Period** starts with the first day of IMP in each cycle in MG0007 and ends after Day 43 or PEOT assessments. All participants in the Safety Set will be considered to have started the Treatment Period. A participant is considered to have completed the Treatment Period of each cycle if assessments from Treatment Period Day 43 are completed.
- **Observation Period** starts with one day after the end of the Treatment Period of each cycle and ends after the final assessments at Day 155 visit. Participants with assessment on any Observation Period day are considered to have started the Observation Period.
- **Non-treatment period** starts with one day after the end of the Observation Period of each cycle and ends before the start of next cycle or the EOS assessment.

A study participant is considered to have completed the study if he/she has completed all phases of the study including the Observation Period and the EOS visit assessments. The end of the study is defined as the date of the last visit of the last participant in the study.

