6.4.2 Assignment of medications to study period

The following rules will be used to assign a medication to a study period:

- **Treatment Period:** a medication will be assigned to the Treatment Period if it has been taken at least once between the first administration of IMP on Day 1 of each study cycle, up to Day 43 or PEOT assessments.

- **Observation Period:** a medication will be assigned to the Observation Period if it has been taken at least once from the day after Treatment Period to the Day 155 visit of each study cycle.

The prior or concomitant medications out of the 2 periods above will be displayed as 'NA' in the listing.

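### SAP 6.4.1 contradicts itself on whether a drug used only in the Non-treatment period is concomitant; under its bullet, such a drug leaves the medication summary and listing

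*SAP*

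**What the plan says.** SAP 6.4.1 gives two classes. Prior "medications will include any medications that started before the first administration of MG0007 IMP". Concomitant covers "any medications that have been taken at least once after the first administration of MG0007 IMP during the Treatment and/or Observation Period".

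The table directly below classifies only by start and finish relative to the first dose. Its second row takes a drug started at any time and finished "After 1st Dose IMP", and labels it concomitant. No study period is mentioned.

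SAP 6.4.2 assigns medications to the Treatment Period or the Observation Period and adds: "The prior or concomitant medications out of the 2 periods above will be displayed as 'NA' in the listing".

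SAP 3.2.2 defines three periods per cycle, not two. The Observation Period ends with the Day 155 visit. The Non-treatment period "starts with one day after the end of the Observation Period of each cycle and ends before the start of next cycle", or before the EOS assessment.

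SAP 6.4 restricts both the ATC/preferred-term summary (Safety Set, entire study) and the listing (FAS) to drugs classed as prior or concomitant. Rescue medication has its own rule there: a start on or after Baseline.

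Protocol Tables 1-2 and 1-3 schedule collection of concomitant medications at the no-treatment visits, and Protocol 6.5.1 states that "dose adjustments are allowed between treatment cycles".

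**The concern.** On the bullet alone, a drug first started after Day 155 of the latest cycle falls between the two classes. It did not start before the first MG0007 dose, so it is not prior. If it is not taken in a later Treatment or Observation Period, it is not concomitant either. Being unclassified, it would appear in neither the summary nor the listing. The Japan-only medication tables in SAP 11.6 follow SAP 6 and would inherit the gap.

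What is at stake is completeness in one part of follow-up. A drug started in the gap is recaptured if it is still in use when the next cycle begins, and is lost if no cycle follows or the course ends first. Time between cycles is a secondary endpoint, and Protocol 9.4.1 reads it as showing how long the effect lasts. A reader who sees a long treatment-free interval would want to know what other therapy was used in it.

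**Working it through.** **End of the bullet's window.** SAP 3.2.2 gives a 6-week Treatment Period and a 16-week Observation Period. Counting from Day 1: 1 + 6×7 + 16×7 = 155. This reproduces the SAP's Day 155.

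**The two rules applied to example courses.** Days count from the first MG0007 dose. Each cycle's window is its first 155 days, or up to the day before the next cycle if that comes sooner.

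| Cycles start on | Drug taken | Prior? | Concomitant by bullet? | Concomitant by table? |
|---|---|---|---|---|
| Day 1 | Day 200–230 | No | **No** | Yes |
| Day 1 | Day 200–400 | No | **No** | Yes |
| Days 1 and 300 | Day 200–230 | No | **No** | Yes |
| Days 1 and 300 | Day 200–400 | No | Yes | Yes |
| Days 1 and 80 | Day 200–230 | No | Yes | Yes |
| Day 1 | Day 100–400 | No | Yes | Yes |
| Day 1 | Day −50 to 400 | Yes | Yes | Yes |

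In the fifth row the second cycle's window runs from Day 80 to Day 80 + 154 = 234, so the course falls inside it. The rules disagree only in the first three rows: a drug started after Day 155 and not in use in any later window. The table keeps every course.

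**Which rule the 'NA' sentence fits.** Under the bullet, a concomitant drug has by definition been taken in one of the two periods, so it could never be listed as 'NA'. The reference in SAP 6.4.2 to concomitant drugs outside both periods has content only under the table's rule.

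**Calendar time outside the window.** For one cycle followed to day T after the first dose, the share is (T − 155)/T. With T taken from the time-in-study cut points in SAP 8.1:

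- T = 360: 205/360 = 57%
- T = 720: 565/720 = 78%
- T = 1080: 925/1080 = 86%

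These values of T are category bounds used as a range, not observed follow-up. For a participant retreated by Day 155 of every cycle, the share before the last cycle is zero.

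**The case against.** The strongest reply is that the SAP does not plan to lose these drugs. A reader of the bullet might infer that it does, but the table and the 'NA' sentence both retain them. Loss occurs only if the bullet is programmed in preference to the table. That stands, so the defect is a contradiction and not a settled exclusion.

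A reader might also infer that gMG therapy added in the gap would go wholly unreported. The documents do not support that:

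- Rescue therapy is summarised under its own rule in SAP 6.4, and again in SAP 11.2 and 11.3.
- SAP 11.1 summarises dose changes in steroids, immunosuppressants and AChE inhibitors during the study, and average daily dose by preferred term at Baseline and last visit.

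SAP 11.1 is only partial cover. It does not say whether a new start counts as a dose change, and a course begun and ended within the gap misses both average-dose time points. It does not replace the SAP 6.4 table.

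Nor does the gap undermine the objective "To assess the need for gMG medications including changes in type and doses". The endpoints listed for it are rescue use, time to rescue and healthcare resource utilization, and none relies on the SAP 6.4 table.

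It is also tempting to argue that the protocol steers medication changes into the excluded time. A dose change removes nobody from a table that counts participants ever taking a drug. Corticosteroids and AChE inhibitors are exempt from the stable-dose request in Protocol 6.5.1. For other drugs the request covers only the first 8 weeks of a 16-week Observation Period, so free adjustment begins inside the bullet's window.

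Finally, all analyses are descriptive, and the time-between-cycles analysis in SAP 9.11 does not use the medication table.

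**Conclusion.** The contradiction is real, and its consequence is narrow. If the bullet is programmed, a non-rescue drug first started in the Non-treatment period and not taken in any later Treatment or Observation Period is left unclassified and drops out of the SAP 6.4 summary and listing. The participants affected are those not retreated and those whose course ends before retreatment. If the table is programmed, nothing is lost.

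The number of drugs or participants affected cannot be found from the documents. The 57% to 86% figures should not be read as a loss rate. They are calendar shares for a participant with a single cycle and no retreatment over 360 to 1080 days, counted from the first dose. They do not carry over directly to MG0004 entrants, who join in the Observation Period and are first dosed on worsening, because time in study in SAP 8.1 runs from the first visit.

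Severity is minor, but this is more than missing detail: one section states two rules that give different outputs from the same data.

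**What to change.** In SAP 6.4.1, end the concomitant definition at EOS instead of limiting it to the Treatment and Observation Periods, so that the bullet agrees with its table.

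In SAP 6.4.2, add a Non-treatment Period category, in place of 'NA', for drugs taken after Day 155 of a cycle and before the next cycle or EOS. 'NA' can remain for drugs used only before the first MG0007 dose.

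Showing the gMG drug classes by period would be useful but is optional.

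The cost is two wording changes in the SAP and one extra level in the period derivation. The data are already scheduled for collection at the no-treatment visits.
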